8.3. Clinical and Safety Records

8.3.1. Adverse events (AEs) monitoring

The subjects' safety is monitored during the entire study. Information regarding adverse events of the study drugs is obtained from physical examination and/or complaint from the subjects. All subjects are instructed to report the occurrence of any discomfort feeling to the Study Physician. An adverse event is any undesirable event associated with the use of drug, whether or not considered drug related. They include any side effect, injury, toxicity, or hypersensitivity reactions, also any undesirable clinical or laboratory change, which does not commonly occur in the subject.

All adverse events, regardless of severity, will be followed up by the Investigator until they are resolved in a satisfactory manner.

8.3.2. Classification of Adverse event (AE) intensity

The intensity of an adverse event is classified according to the following criteria:

- Mild : awareness of the signs and symptoms but is easily tolerated
 Moderate : sufficient discomfort to cause interference with normal activities
 Severe : incapacitating with inability to perform normal activities.

The intensity of any AE which occurs during the study will be documented in the CRFs.

8.3.3. Classification of Adverse event (AE) causality

The causal relationship of an adverse event is classified to the following criteria:

Causality term	Assessment criteria, all points should be reasonably complied with
Definite / certain	
 Event with plausible time relationship with drug intake Cannot be explained by disease or other drug Event definite pharmacologically or phenomenologically (i.e. an objective and specific medical disorder or recognized pharmacological phenomenon)
Probable/likely	
 Event with reasonable time relationship to drug intake Unlikely to be attributed to disease or other drugs
Possible	
 Event with reasonable time relationship to drug intake Could also be explained by other disease or other drug Information on drug withdrawal may be lacking or unclear
Unlikely	
 Event with a time to drug intake that makes a relationship improbable (but not impossible) Disease or other drugs provide plausible explanations
Unrelated	
 Where there is sufficient information to conclude no causal relationship

8.3.4. Serious adverse event (SAE) reporting

A serious adverse event is any adverse event that is fatal, is life-threatening, requires or prolongs hospitalization, results in persistent or significant disability or incapacity, or is a congenital anomaly/birth defect, or other medically important events which may not life threatening/cause death/ hospitalized but may jeopardize the patient or may require intervention to prevent one of the outcomes above.

Life-threatening SAE means that the patient is at immediate risk of death from the events as it occurred. It does not include an event that, has it occurred in a more serious form, may have caused death.

Requires hospitalization SAE is defined as hospital admission if required for treatment of the adverse event.

In the event of a SAE, for reporting purposes, Principal Investigator or Study Director may be required to break the individual randomization code of the related subject. Record of this decode will be maintained.

If any SAE occurs, the Investigator will notify the sponsor within 24 hours and to Ethic Committee within 3 calendar days. The sponsor's responsibility is to report a SAE to the regulatory authority after the investigator's note has been delivered within 15 calendar days.

Any SAE will be reported to:

[name]
 PT. Sydna Farma
 [name]
 [name]
 Indonesia
 [contact]
 [contact]
 Email : [contact]

The Investigator is responsible to assure the care or hospitalization of the subjects suffering from study-related adverse events, and the cost for the treatment will be covered by the sponsor.

8.4. Pharmacokinetics parameter

The area under the cyproterone acetate and ethinyl estradiol concentration versus time curve from 0 to 72 hours (AUC_t) is calculated using trapezoidal method.

The total area under the curve from administration to infinity (AUC_{inf}) is calculated as the sum of AUC_t and the residual area (C_t divided by k_e , where C_t is the last measured concentration and k_e is the apparent terminal elimination rate). k_e is estimated by log-linear regression from at least 3 concentrations at the terminal portion of the log-transformed concentration plot. The $t_{1/2}$ is calculated by dividing 0.693 by k_e .

The following equation is used for calculation:

$$AUC_{inf} = AUC_t + C_t/k_e$$

$$t_{1/2} = 0.693/k_e$$

The peak plasma concentration (C_{max}) and the time to attain peak (t_{max}) are determined by inspection of the individual plasma concentration-time profiles of the drug (the observed values).

8.5. Statistical evaluation

Bioequivalence of the two drug formulations is assessed by calculating individual AUC_t and C_{max} values. The mean ratio (test/reference) of the ln-transformed data and their 90% confidence intervals is analyzed with a parametric method (analysis of variance/ANOVA) using Equiv Test[®] version 2.0 (Statistical Solution Ltd., Saugus. MA, USA) or manual calculation which has been validated to Equiv Test[®]

90% confidence intervals (90% CIs) are calculated using the following equation :

$$(90\% \text{ CI})_{diff} = \text{difference} \pm t_{0.1 (n-2)} \times SE_{diff}$$

$$\text{difference} = \text{mean of ln T} - \text{mean of ln R}$$

PharmaMetric Labs

n = number of subject

$\alpha = 0.05$

$SE\ diff = (\frac{1}{2}MS_{residual} \times (1/nTR + 1/nRT))^{\frac{1}{2}}$

(90% CI) ratio = anti ln (90% CI)_{diff} X 100%

The two products are considered bioequivalent when the 90% confidence interval of the cyproterone acetate and ethinyl estradiol geometric mean ratio between test and reference product falls within the range of 80.00 - 125.00% for AUC_t and C_{max}.

If a pre-dose concentration of cyproterone acetate and ethinyl estradiol is detected, the subject's data can be included in the pharmacokinetic and statistical analysis without adjustment, if the pre-dose concentration is equal to or less than 5% of the C_{max} value of the corresponding period. If the pre-dose concentration is greater than 5% of the C_{max} value, the subject's data will be dropped from all pharmacokinetic and statistical evaluations of cyproterone acetate and ethinyl estradiol.

Subjects who lack of any measurable concentrations, or have only very low plasma concentrations of cyproterone acetate and ethinyl estradiol for the reference medicinal product, will be excluded from statistical analysis. According to EMA Guidance (CPMP/EWP/QWP/1401/98 Rev.1/Corr**), a subject is considered to have very low plasma concentrations if its AUC is less than 5% of reference medicinal product geometric mean, calculated without inclusion data from the outlying subject. Data (concentrations and pharmacokinetic parameters) from these excluded subjects will be presented but excluded from descriptive statistics. If the study is continued to the second stage, the 94.12% confidence intervals (94.12% CIs) are calculated using $\alpha = 0.0294$.

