Dates of Analytical Portion :

Method Validation : December 2018
Sample Analysis : After completion of Period 1 and 2

Objectives

The objective of this study is to investigate whether 2 mg cyproterone acetate and 0.035 mg ethinyl estradiol film-coated tablet (**Elzsa[®]**) manufactured by PT. Sydna Farma is bioequivalent to its reference product, Diane[®]-35 sugar-coated tablet manufactured by Bayer Weimar GmbH, Germany for Bayer Pharma AG, Germany, **imported by PT. Bayer Indonesia, Depok, Indonesia.**

PharmaMetric Labs**Study Centre, Clinical Study Laboratory, Analytical Laboratory, Pharmacokinetics and Statistical Analysis Laboratory:**

PT. Pharma Metric Labs
 [name]
 [name]
 [name]
 Indonesia
 [contact]
 [contact]

Medical Screening (blood and urine) Laboratory:

Pramita Clinical Laboratory
 [name].
 [contact]
 [contact]

Sponsor

PT. Sydna Farma
 [name]
 [name]
 Indonesia
 [contact]
 [contact]

Study design

Randomized, single blind, two period, single dose, cross-over study with three weeks washout period in 24 healthy female subjects under fasting condition.

The overall clinical study requires approximately 8 weeks to be completed. The drug allocation information is limited to the Data Management Officer only.

If the above study results in the conditions below, the study could be continued to the second stage with a minimum 12 subjects addition. The second stage study's pharmacokinetics will be statistically analyzed within 94.12% confidence interval. The conditions are:

1. The first stage study has demonstrated bioequivalence, but the number of subjects is not adequate to fulfill 80% power study calculated from the intra subject CV of AUC_t obtained; OR
2. The first stage study has resulted in non-bioequivalence but the geometric mean ratio of the AUC_t falls within 90-110%, and it is probable to have bioequivalence result if the study is continued to the second stage.

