8. INVESTIGATIONAL PLAN

8.1. Study design

Randomized, single blind, two period, single dose, cross-over study with three weeks washout period in 24 healthy female subjects under fasting condition.

The overall clinical study requires approximately 8 weeks to be completed. The drug allocation information is limited to the Data Management Officer only.

If the above study results in the conditions below, the study could be continued to the second stage with a minimum 12 subjects addition. The second stage study's pharmacokinetics will be statistically analyzed within 94.12% confidence interval. The conditions are:

1. The first stage study has demonstrated bioequivalence, but the number of subjects is not adequate to fulfill 80% power study calculated from the intra subject CV of AUC_t obtained; OR
2. The first stage study has resulted in non-bioequivalence but the geometric mean ratio of the AUC_t falls within 90-110%, and it is probable to have bioequivalence result if the study is continued to the second stage.

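### Stage 1 is decided on an unadjusted 90% CI and only stage 2 on a 94.12% CI, so the two-stage rule does not hold the false-bioequivalence risk at 5%

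*Combined protocol and SAP*

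**What the plan says.** Section 8.5 sets the decision rule: "The two products are considered bioequivalent when the 90% confidence interval of the cyproterone acetate and ethinyl estradiol geometric mean ratio" lies within 80.00-125.00% for AUC_t and Cmax. The interval uses the t value for 0.1 two-sided on n - 2 degrees of freedom, that is, 5% per side. The section closes with: "If the study is continued to the second stage, the 94.12% confidence intervals (94.12% CIs) are calculated using" α = 0.0294.

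Section 8.1, repeated in the synopsis, says that "the study could be continued to the second stage with a minimum 12 subjects addition" in either of two cases:

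- Condition 1: "The first stage study has demonstrated bioequivalence, but the number of subjects is not adequate to fulfill 80% power study", judged from the observed AUC_t CV.
- Condition 2: "The first stage study has resulted in non-bioequivalence but the geometric mean ratio of the AUC_t falls within 90-110"%. This condition has a second part, to which the plan attaches no number: "it is probable to have bioequivalence result if the study is continued to the second stage".

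On the stage-2 analysis, both places say only: "The second stage study's pharmacokinetics will be statistically analyzed within 94.12% confidence interval". The plan states no overall error rate, no maximum for stage 2 and no rule on pooling the stages.

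**The concern.** A 90% CI rule carries a 5% risk of passing a product that sits at the equivalence limit. If stage 1 spends all of that 5% and a failed study may be tested again, any success at the second look adds to it. A stricter second interval makes the addition smaller but not zero.

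Four open terms decide how large it is:

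1. The 90-110% gate applies to AUC_t only. For Cmax the sole limit is that success is *probable*, with no number.
2. It is not stated whether stage 2 is analysed with stage 1 or alone.
3. Stage 2 has a minimum of 12 subjects and no maximum.
4. Under condition 1 a study that has passed may continue, but the plan does not say which result then counts.

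The exposed case is Cmax near the limit with AUC_t inside the gate. The pilot in section 5.2, Table III, illustrates it for ethinylestradiol: Cmax 107.45/86.37 = 1.244 and AUC_t 1020.47/987.75 = 1.033. With six subjects and ratios of arithmetic means, this illustrates the case; it does not predict the result.

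**Working it through.** **The plan's own figure.** 1 - 2 × 0.0294 = 0.9412, so the 94.12% interval matches α = 0.0294. Likewise 1 - 2 × 0.05 = 0.90 for stage 1.

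**Inputs.** From the plan: n1 = 24, limits 80.00-125.00%, a 90% CI at stage 1, a 94.12% CI at stage 2, the AUC_t gate of 0.90-1.10, and n2 of at least 12. Assumed: n2 = 12, 24 or 48; pooled data; Cmax true ratio 1.25 with CV 10-30%; AUC_t true ratio 1.033 with CV 14.5%. The AUC_t CV comes from Table I (n = 30, taken as a balanced 2×2 crossover):

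- Half-width = ln(104.66/92.21)/2 = 0.0633.
- SE = 0.0633 / t(0.95; 28 df) = 0.0372.
- Residual variance = 0.0372² × 30/2 = 0.0208.
- CV = √(exp(0.0208) - 1) = 14.5%.

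The same steps give 9.9% for ethinylestradiol Cmax, and 7.1% and 14.2% for cyproterone AUC_t and Cmax.

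**Check 1: known variance, gate always open, pooled data.** The two test statistics correlate at √(24/(24 + n2)). With p1 and p2 the two nominal levels, the overall error is p1 + p2 - P(pass both).

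| n2 | Correlation | As written: 5% + 2.94% - P(both) | 94.12% at both looks: 2 × 2.94% - P(both) |
|---|---|---|---|
| 12 | 0.816 | 7.94 - 1.84 = 6.10% | 5.88 - 1.39 = 4.49% |
| 24 | 0.707 | 7.94 - 1.40 = 6.54% | 5.88 - 1.03 = 4.85% |
| 48 | 0.577 | 7.94 - 1.02 = 6.92% | 5.88 - 0.72 = 5.16% |

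If stage 2 is analysed alone the looks are independent. The ceiling is then 5% + 95% × 2.94% = 7.8% as written, and 2.94% + 97.06% × 2.94% = 5.8% with 94.12% at both looks.

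**Check 2: simulation of the written rule** (1 million runs per cell, AUC_t gate applied, pooled test on N - 4 df). Stage 1 alone gives 5.0%. *Probable* is read as a minimum projected power for Cmax, computed from the observed ratio and CV at α = 0.0294; this reading is an assumption.

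| Reading of *probable* | 12 added | 24 added | 48 added |
|---|---|---|---|
| Not binding | 6.0% | 6.4-6.5% | 6.8% |
| At least 20% | 5.8-5.9% | 6.0-6.1% | 6.2-6.3% |
| At least 50% | 5.1-5.2% | 5.4-5.5% | 5.7-5.8% |
| At least 80% | 5.0% | 5.0% | 5.1-5.2% |

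**AUC_t itself at the limit.** The gate then does most of the work. If a stage-1 pass stands, the rate is 5.0% at CVs up to 20%, peaks at about 5.5% near CV 35%, and is below 5% at CV 50%.

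**Condition 1.** With 24 subjects, power is 80% up to a CV of 23.2% (ratio 0.95 assumed). At a true AUC_t CV of 14.5% the condition would trigger in about 0.01% of studies, so it does not alter these Cmax results.

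**The case against.** The strongest reply is that the 6-7% figures set aside a written condition: continuation requires that success is probable, and it is optional. Given a strict meaning, that condition removes nearly all of the excess, and at the 12-subject minimum no pooled scenario exceeds 6.1%. This is correct, but the plan gives the word no value, so the protection cannot be counted on. The value could be chosen after stage 1 is seen.

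A second reply is that the real gap is the missing Cmax gate. Keeping the 90% CI and applying 90-110% to Cmax as well gives 5.0% at Cmax CVs of 10-20% and up to 5.2% at 30%, with no loss of stage-1 power. That would be a large improvement and shows where most of the excess arises. It still leaves stage 1 spending the full 5%, so control depends on the CV.

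Third, the pilot is weak evidence. Its tables name the test drug Lydia, not Elzsa, and the larger study in Tables I-II, of another test product, has Cmax ratios of about 0.96 and 0.92. This stands, but the finding does not rest on the pilot, because error control is judged at the limit.

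Fourth, a fixed cap of 24 presumes 24 evaluable stage-1 subjects. If the addition is chosen between 12 and 24 after seeing stage 1, the worst case is 4.99%, 5.05% and 5.10% with 22, 20 and 18 evaluable. A fixed addition of 24 stays at 4.9-5.0%. This is a useful refinement and is taken up in the fix.

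**Conclusion.** The concern holds. The adjustment is applied at one of two looks, and nothing elsewhere in the plan corrects this. With pooled data and Cmax at the limit, the risk of passing a non-equivalent product is between 5% and about 7%, depending on the size of stage 2 and the meaning given to *probable*. If stage 2 were analysed alone it could reach 7.8%. The excess is small or absent when AUC_t is the parameter at the limit, or when *probable* is read strictly. Under high CVs, where stage 1 rarely passes, the rate can fall below 5%.

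The CVs, the stage-2 sizes and pooling are assumptions, because the plan gives no planning CV, maximum or pooling rule. The excess is moderate, but it lies in the primary decision rule and cannot be repaired credibly once stage-1 results are known.

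**What to change.** Amend the synopsis, 8.1 and 8.5 together, before stage-1 data are available:

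1. Use the 94.12% CI (α = 0.0294) for the stage-1 decision as well as the stage-2 decision.
2. State that stage 2 is analysed on the pooled data of both stages, with stage in the ANOVA.
3. Limit the addition to 12-24 subjects, and to no more than the number evaluable in stage 1.
4. Replace *probable* with a number, for example projected power of at least 50% for every parameter that failed.
5. State that a stage-1 pass at 94.12% is final, or delete condition 1.

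With items 1-3 and 24 evaluable stage-1 subjects, the rate is 4.4-4.5% with 12 added and 4.7-4.9% with 24. It is at most 4.9% for any size from 12 to 24 chosen after seeing stage 1. The cap and the pooling are both needed: with 48 added the rate is 5.0-5.2%, with the size chosen freely from 12 to 48 up to 5.4%, and without pooling up to 5.8%.

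The cost is protocol wording and some stage-1 power at n = 24:

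| Case | 90% CI | 94.12% CI |
|---|---|---|
| Ratio 0.95, CV 14.5% | 99.1% | 98.0% |
| Ratio 0.95, CV 20% | 89.6% | 83.6% |
| Ratio 0.917, CV 14.2% (cyproterone Cmax, Table II) | 94.5% | 90.6% |
| Ratio 0.917, CV 20% | 74.8% | 65.5% |
| All four endpoints at Table I-II values, treated as independent | 94.5% | 90.6% |

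A capped second stage can recover part of this. Alternatives are to keep the 90% CI and delete the second stage, or to prespecify another split of α, with any gate on Cmax, shown to hold 5% overall.

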8.6. Assay methodology and validation

8.6.1. Assay method description

Plasma concentration of cyproterone acetate and ethinyl estradiol is measured using a validated LC-MS/MS method. Plasma is first spiked with internal standard solution, then further mixed using vortex. The drug is then extracted with organic solvent. The organic layer is transferred to a clean glass tube and evaporated to dry under nitrogen stream in a water bath. The residue is then reconstituted with organic solvent and an aliquot is injected into the LC-MS/MS system. The LLOQ is 0.4 ng/ml and 4.99 pg/ml for cyproterone acetate and ethinylestradiol, respectively.

8.6.2. Instruments

Blood samples and standards are transferred or taken using Soccorex multipipette. The standard is weighed using a Mettler Toledo XP 26DR micro analytical balance. A Hettich Rotofix 32A centrifuge is used to separate plasma and the supernatant liquid mixture. A Caliper TurboVap LV dwell that applies nitrogen is used to evaporate the solvent.

The LC-MS/MS system included an Acquity™ solvent delivery manager, Acquity™ sample manager and TQD™ MS/MS from Waters Corp. Data acquisition, peak integration and calibration were performed by Mass Lynx software from Waters Corp. Its separation is performed on a C18 column and protected by suitable guard column.

The chromatographic system was as follows:

Column	: Waters Acquity BEH C ₁₈ 1.7 μ m, 2.1 x 50 mm
Mobile phase	: Acetonitrile : 0.1% Formic acid in H ₂ O (80:20)
Flow rate	: 0.3 mL/minute

8.6.3. Quantification

The calculation of drug level is performed using cyproterone acetate and ethinyl estradiol calibration curve based on the peak ratios of the analyte versus internal standard used at the specified concentrations (1 blank, 1 zero, and 6-8 nonzero). The result of the calibration curve is a linear regression line (statistically calculated).

8.6.4. Validation

The method validation is performed according to international guideline. The assay method is validated to demonstrate adequate selectivity, linearity, accuracy and precision, carry-over, matrix effect, dilution integrity, LLOQ, anticoagulant effect and stability.

8.7. Quality assurance

The Quality Assurance (QA) department reviews BA/BE study conduct at regular intervals and maintain written and signed records of findings and problems related to the study. Any problem found during review, which may affect the integrity of the study data, will be brought to the attention of the Principal Investigator.

The QA department or sponsor representative will assure that no deviations from the approved protocols or standard operating procedures without proper authorization and documentation. The QA department will review the analytical report and the bioequivalence study report to assure that those reports accurately reflects the raw data.

8.8. Others**8.8.1. Clinical records**

All data generated during the study is directly entered into the CRF accurately. All entries must be legibly recorded in blue ink, while corrections are made by crossing the wrong entry with a single line and writing the correct entry. All corrections must be initialed and dated.

Data from analytical laboratory are transcribed into appropriate forms and recorded. Chromatograms are treated as raw data, and data derived from statistical and pharmacokinetic analysis are archived. Personnel involved in the study, monitors from sponsor, or regulatory representatives have access to the source data. All data are liable for quality assurance audit. Copies of all pertinent information (data) are retained by PT. Pharma Metric Labs for at least 5 years after study completion. Additional considerations are made for complying with the applicable local laws and guidelines.

8.8.2. Documents necessary to start the study

The following documents are necessary before starting the study:

- Study protocol,
- Information for subjects and informed consent,
- Case Report Form,
- Ethics Committee/Institutional Review Board written approval of the study protocol & information for subjects,
- Study drug certificate of analysis, comparative dissolution profiles and letter of confirmation,
- NADFC written approval of the study protocol
- Clinical Trial Import License (if required)

8.8.3. Ethics approval and amendments

The protocol, the informed consent statement, and advertisement are reviewed by the Independent Ethics Committee of the Medical Faculty, University of Indonesia. Any modification of the protocol which may have any impact on the conduct of the study, potential benefit of the study, or may affect subjects' safety, including changes of the study objective, study design, study population, sample size, study procedure, or significant administrative aspects will require a formal amendment to the protocol. Such amendment has to be agreed upon by the sponsor, the responsible investigator and the Ethics Committee prior to implementation.

Minor administrative changes of the protocol are minor corrections and/or clarifications that have no effect on the way of the study is conducted. These minor administrative changes will be agreed upon by the sponsor and the responsible investigator and will be documented in a memorandum. The Ethics Committee may be notified of the minor administrative changes at the discretion of the responsible investigator.

